Erythroid response is defined in those who with a pretreatment hemoglobin of < 9.0 g/dL as an increase in hemoglobin concentration of ≥ 1.5 g/dL above baseline without transfusion, or reduction in the transfusion unit by at least 4 units for 8 consecutive weeks compared with the pretreatment transfusion requirement in the previous 8 weeks prior to the first administration of AMG531 (Day -55 to Day 1).

Neutrophil Response

Neutrophil response is defined in those with a pretreatment absolute neutrophil count (ANC) of $< 0.5 \times 10^9/L$ as a 100% increase over the baseline, or an increase in ANC of $> 0.5 \times 10^9/L$ in subjects with a pretreatment ANC of $< 1.0 \times 10^9/L$.

Baseline

Baseline values are defined as the values obtained before dosing AMG531 on Study Day 1. Data obtained during the screening period will serve as baseline values for those not measured or reported on Study Day 1. If multiple evaluations are performed during the screening period for a particular test, with the exception of platelet count, the values measured closest to the first administration of AMG531 will be considered as the baseline values (if hemoglobin concentration at Study Day 1 is within 28 days after RBC transfusion, hemoglobin concentration determined during the screening period will be used as baseline hemoglobin).

Baseline Platelet Count

Baseline platelet count is defined as the mean of two lowest platelet counts measured in 8 weeks prior to enrollment. Platelet count that is obtained within 7 days after platelet transfusion will not be used. The baseline platelet according to the definition of protocol Master Ver1.1 (The mean of two lowest platelet counts measured in 8 weeks prior to enrollment. Platelet count that is obtained within 3 days after platelet transfusion will not be used.) will be also collected .

Platelet Transfusion

Platelet transfusion given due to platelet count of $< 10 \times 10^9/L$ (prophylactic transfusion) or due to bleeding (therapeutic transfusion).

RBC Transfusion

RBC transfusion given due to the hemoglobin concentration of ≤ 9.0 g/dL or due to symptomatic anemia

Adverse Drug Reaction

Adverse events of which causal relationship to the investigational product cannot be ruled out (any events assessed to be other than “unlikely” or “not related”).

Study Duration

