Study duration of each subject in this study is specified as the period from the day of obtaining written informed consent through the end of examinations on completion of treatment (or withdrawal).

Observation and Examination Period

In this study, Week 1 (Day 1) is defined to be the day of initial administration of AMG531. Initial dose evaluation period is defined to be the period from Week 1 to Week 8, Extension period is the period from Week 9 to Week 52, and Long-term treatment period is the period from Week 53 to Week 156.

Aplastic Anemia with Refractory Thrombocytopenia

Aplastic anemia with thrombocytopenia defined as platelet count of $\leq 30 \times 10^9/L$ that does not respond to the immunosuppressive therapy (ATG + cyclosporine), or relapsed after having showed response.

Transfusion Independence

Achieving platelet or RBC transfusion free period of at least 8 consecutive weeks.

Tri-lineage response

Tri-lineage response is defined in those achieving platelet response, erythroid response, and neutrophil response all together.

Normal level

Normal level is defined as platelet counts $>50 \times 10^9/L$, hemoglobin concentration >10.0 g/dL, and neutrophil counts $>1.0 \times 10^9/L$

Stable response

Stable response is defined as platelet counts $\geq 30 \times 10^9/L$, hemoglobin concentration ≥ 9.0 g/dL, and neutrophil counts $\geq 0.5 \times 10^9/L$ maintained during dose tapering or discontinuation without transfusion

Cytogenetic abnormality

Any cytogenetic abnormalities newly emerged during or after the initiation of AMG531 treatment

PROTOCOL SYNOPSIS

I TITLE

A phase 2, Randomized, Open-Label, Parallel, Comparative, Dose-Finding Study to Evaluate the Efficacy and Safety of AMG531 in Aplastic Anemia (AA) Subjects with Thrombocytopenia Refractory to Immunosuppressive Therapy

[figure not shown]
II STUDY OBJECTIVES

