- The proportion of subjects who become platelet transfusion independent during the initial dose evaluation period, Week1 through Week 12, Week 1 through Week 16, Week 1 through Week 24, Week 1 through Week 52, Week 1 through Week 104, and Week1 through Week 156
- The proportion of subjects achieving erythroid response and/or neutrophil response during the initial dose evaluation period, Week1 through Week 12, Week 1 through Week 16, Week 1 through Week 24, Week 1 through Week 52, Week 1 through Week 104, and Week1 through Week 156
- Duration of platelet response
- Time to platelet response
- Changes in platelet count, hemoglobin concentration, and neutrophil count as continuous variables
- Changes in bone marrow cellularity and reticulin grade
- Changes in GIMEMA bleeding scale
- The proportion of subjects achieving tri-lineage responses
- The proportion of subjects able to discontinue study drugs after achieving normal level for 8 consecutive weeks without transfusion.
- Duration of study drug discontinuation while maintaining stable response

VI-2 Pharmacokinetics

- Serum AMG531 concentration
- Pharmacokinetic parameters

VI-3 Safety

- Adverse events
- Antibody formation against AMG531 and TPO

VI-4 Exploratory

- The changes of primitive hematopoietic stem and progenitor cells
- The changes of progenitor cell pool (colony forming cell assay)
- The changes of stromal cell (colony forming unit fibroblast assay)
- Cytokine assay (IL-2, IL-6, IL-10, IL-12, IL-17, IFN- γ , TNF- α)

VII CRITERIA FOR SUBJECT WITHDRAWAL

Any of the following circumstances will result in the subject being withdrawn from the study:

- 1) The subject is found to be ineligible for participation in this study due to violations in the inclusion or exclusion criteria specified in the study protocol;
- 2) The subject decides to discontinue his/her participation in the study;
- 3) The subject becomes unable to undergo necessary observations or examinations;
- 4) The subject who does not achieve a platelet response after 8-week treatment with AMG531 20 $\mu\text{g}/\text{kg}$ QW;
- 5) The investigator considers that the subject should be withdrawn from the study due to an adverse event (including progression of the primary disease);
- 6) The subject received any of the prohibited concomitant medications or treatments;
- 7) The subject becomes pregnant or wants to have children during the study;

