5.2 Inclusion criteria

Subjects may be included in the study if they meet all of the following criteria:

- 1) Patients who have provided written informed consent of their free will to participate in this clinical study. Written informed consent must be obtained prior to performing any study-related procedure
- 2) The subject is able and willing to comply with study procedures and follow-up as described in the protocol and ICF
- 3) Males and female subjects ≥ 19 years of age at the time of obtaining informed consent
- 4) Eastern Cooperative Oncology Group (ECOG) performance status (PS) score of ≤ 2 at the time of screening
- 5) Diagnosis of AA, confirmed by bone marrow and cytogenetic studies
- 6) Patient who is refractory to immunosuppressive therapy (IST)
- 7) Prior treatment with at least one course of horse or rabbit anti-thymocyte globulin (ATG) with cyclosporine
- 8) Thrombocytopenia defined as platelet $\leq 30 \times 10^9/L$
- 9) Fulfilling all of the following criteria in the screening examination
 - T-Bilirubin ≤ 1.5 times the upper limit of the laboratory normal range
 - ALT and AST ≤ 3 times the upper limit of the laboratory normal range
 - Creatinine ≤ 2.0 mg/dL

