6.2.3 Recording concomitant medication and therapy in electronic Case Report Form (eCRF)

All concomitant medication and therapy that a subject received during the period after enrollment through to the end of the study will be recorded on electronic case report form (eCRF) by the investigator with the following information for each concomitant medication and therapy: name of drug, route of administration, duration of treatment and justification for the administration. Agents not intended for medical treatment such as rehydration including saline solution, dissolving solution, or contrast medium for imaging diagnostics are not required to be recorded.

Platelet transfusions given between the period within 56 days (Day -55) prior to the first administration of AMG531 (Day 1) and RBC transfusion given between the period of within 26 weeks (Day -181) prior to the first administration of AMG531 (Day 1) through to the end of study will be recorded in eCRF, including date of each transfusion, volume of transfusion (unit and mL), platelet count or hemoglobin concentration before each transfusion, and reason for each transfusion.

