8.2 Observations/assessments/examinations and schedule

8.2.1 Screening examinations

A signed and dated IRB approved informed consent must be obtained before any study specific procedures are performed. Procedures that are part of routine care are not considered as study specific procedures.

The screening period begins on the date of subject signed the IRB approved informed consent and continues until the date of first administration of AMG531. The following screening examination will be conducted within 4 weeks prior to the first administration of AMG531 (Week -4 to Day 1). Retesting during this period may be performed as needed.

Subjects who fail screening will be allowed to be re-screened if a remediable cause for the original screen failure is found.

- 1) Baseline characteristics: date on which the subject is diagnosed with AA, severity of AA (Appendix 2), previous treatments for AA (duration and sort of treatment), baseline platelet count, platelet transfusion in the previous 8 weeks prior to the first administration of AMG531 (Day -55 to Day 1), RBC transfusion in the previous 26 weeks prior to the first administration of AMG531 (Day -181 to Day1), concomitant medications, medical history, current complications, date of birth, gender, weight, and height, baseline platelet count according to the protocol Master Ver1.1 (The mean of two lowest platelet counts measured in 8 weeks prior to enrollment. Platelet count that is obtained within 3 days after platelet transfusion will not be used)
- 2) Bone marrow biopsy and aspiration with cytogenetics (M/E ratio, cellularity of bone marrow, reticulin grade (reticulin stain/trichrome stain (Appendix 1)), iron stain, narrative pathology report, cytogenetic report and exploratory test described in section 3.3.4)
- 3) Pregnancy test (excluding male subjects and female subjects underwent oophorectomy or hysterectomy or those who are non-childbearing potential i.e., menstrual periods have been absent for at least 12 months)
- 4) ECOG PS

- 5) Vital signs (systolic blood pressure, diastolic blood pressure and pulse rate)
- 6) Hematology (WBC, RBC, Hb, Ht, MCV, MCH, MCHC, PLT, Ret and WBC with differential count)
- 7) Serum chemistry (TP, ALB, T-Bil, D-Bil, AST, ALT, ALP, LDH, γ -GTP, T-Cho, UA, BUN, Cr, Na, K, Ca, P and Cl)
- 8) Blood iron-related parameters (Fe, TIBC, UIBC, TSAT and ferritin)
- 9) Blood coagulation and fibrinolysis (PT-INR, APTT and D-dimer)
- 10) Folic acid and vitamin B₁₂

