12.1.1.2 Secondary endpoint

The secondary endpoint will be evaluated based on the PPS. The proportion of subjects with a platelet response in any time during the initial dose evaluation period, Week 1 through Week 12, Week 1 through Week 16, Week 1 through Week 24, and Week 1 through Week 52 or the proportion of subjects achieving platelet transfusion independency during the initial dose evaluation period, Week 1 through Week 12, Week 1 through Week 16, Week 1 through Week 24, Week 1 through Week 52, Week 1 through Week 104, and Week 1 through Week 156 will be calculated in the same manner as the primary variables. Platelet transfusion independence is defined as achieving transfusion free period of at least 8 consecutive weeks.

The proportion of subjects with erythroid and/or neutrophil response during the initial dose evaluation period as well as in Week 1 through Week 12, Week 1 through Week 16, Week 1 through Week 24, Week 1 through Week 52, Week 1 through Week 104, and in

Week1 through Week 156 will be calculated in the same manner as the primary variables. An erythroid response is defined as achieving an increase in hemoglobin concentration of ≥ 1.5 g/dL above baseline without transfusion or reduction in the transfusion unit by at least 4 units for 8 consecutive weeks compared with the pretreatment transfusion requirement in the previous 8 weeks prior to the first administration of AMG531 (Day -55 to Day 1). A neutrophil response is defined in those with ANC of $< 0.5 \times 10^9/L$ as a 100% increase over the baseline, or an increase in ANC of $> 0.5 \times 10^9/L$ in subjects with a pretreatment ANC of $< 1.0 \times 10^9/L$.

Time to platelet response and duration of platelet response will be summarized.

The change in platelet counts, hemoglobin concentrations, and neutrophil counts from baseline will be summarized at each scheduled visit. For the transfusion, only the platelet transfusion given due to platelet count of $< 10 \times 10^9/L$ (prophylactic transfusion) or due to bleeding (therapeutic transfusion) and RBC transfusions of which hemoglobin concentration is ≤ 9.0 g/dL or due to symptomatic anemia will be included in the response assessment.

The changes in bone marrow cellularity and reticulin grade will be summarized by each subject based on the test reports. The changes in the GIMEMA bleeding scale will be summarized.

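### Section 12.1.1.2 drops the haemoglobin limit from erythroid response; separately, the platelet transfusion independence rate needs a split by baseline transfusion status to be interpretable

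*Combined protocol and SAP*

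**What the plan says.** **Erythroid response.** The Definition of Terms opens: "Erythroid response is defined in those who with a pretreatment hemoglobin of < 9.0 g/dL". It then gives two routes to response: a rise of at least 1.5 g/dL without transfusion, or a fall of at least 4 transfused units over 8 weeks against the 8 weeks before treatment. Section 12.1.1.2 repeats both routes but not the haemoglobin limit. Its next sentence keeps the limits for neutrophil response (pretreatment ANC below 0.5 or below 1.0 × 10^9/L). Tri-lineage response, in the same section, requires platelet, erythroid and neutrophil response together. The Definition of Terms counts an "RBC transfusion given due to the hemoglobin concentration of" 9.0 g/dL or less, or one given for symptomatic anaemia.

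**Platelet transfusion independence.** The Synopsis (VI-1) and Section 3.3.1.2 name the endpoint as "The proportion of subjects who become platelet transfusion independent during the initial dose evaluation period" and six longer windows, up to Week 156. The Definition of Terms gives the rule as "Achieving platelet or RBC transfusion free period of at least 8 consecutive weeks", and Section 12.1.1.2 as "Platelet transfusion independence is defined as achieving transfusion free period of at least 8 consecutive weeks". Only platelet transfusions given for a count below 10 × 10^9/L, or for bleeding, enter the response assessment. Eligibility (Section 5.2) has "Thrombocytopenia defined as platelet" count of 30 × 10^9/L or less and does not ask for prior transfusion. Sections 6.2.3 and 8.2.1 record platelet transfusions over the 8 weeks before the first dose, but neither statement of the rule uses that record.

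Secondary endpoints are analysed on the PPS, with the FAS as a robustness check. Section 12.2 sets no significance level.

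**The concern.** (A) Two current texts define the same endpoint differently. A programmer working from Section 12.1.1.2 counts erythroid responders whom the Definition of Terms leaves out. The erythroid rate, and for some subjects the tri-lineage rate, then depends on which text is followed.

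(B) The endpoint's name describes a change of status, but the rule tests only for an 8-week run without transfusion. A subject who did not need platelet transfusions beforehand and still does not need them is a success with nothing having changed. If such subjects are enrolled, the rate partly reports who came into the trial. The study is meant to support a recommended dose, and with no hypothesis test the descriptive proportions carry that argument, so readers need to know what this one measures.

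**Working it through.** The documents give no figure for either point, so there is none to reproduce. Part A is a comparison of texts. Part B is arithmetic on stated assumptions.

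**A. Erythroid response**

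| | Definition of Terms | Section 12.1.1.2 |
|---|---|---|
| Pretreatment Hb limit | below 9.0 g/dL | none |
| Rise without transfusion | ≥ 1.5 g/dL | ≥ 1.5 g/dL |
| Transfusion reduction | ≥ 4 units over 8 weeks | same |
| Neutrophil response: ANC limits | stated | stated |

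1. Untransfused subject, Hb 11.0 to 12.5 g/dL: the rise is 12.5 − 11.0 = 1.5 g/dL. This is a responder under 12.1.1.2. Under the Definition of Terms, 11.0 is not below 9.0, so the subject falls outside.
2. Illustration for an arm of 8. Assume 2 subjects with Hb of 9.0 or more, of whom 1 rises by at least 1.5 g/dL, and 1 responder among the other 6. Section 12.1.1.2 gives 2/8 = 25%. The Definition of Terms gives 1/8 = 12.5% on all PPS subjects, or 1/6 = 16.7% on those evaluable at baseline.
3. Tri-lineage response: both neutrophil routes require pretreatment ANC below 1.0 × 10^9/L. The conflict therefore carries over only for subjects with Hb of 9.0 or more and ANC below 1.0.
4. Transfusion-reduction route: RBC units given at exactly 9.0 g/dL, or for symptomatic anaemia, qualify. A subject with pretreatment Hb of 9.0 or more can therefore have qualifying units, and it matters whether the limit covers this route.

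**B. Platelet transfusion independence**

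Inputs: n = 8 per arm and 32 in total (Section 3.5.1). The share u of subjects with no qualifying transfusion at baseline who stay that way is not given; 0–75% is assumed. The conversion rate p among previously transfused subjects is also assumed.

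1. The pre-treatment record runs from Day −55 to the day before Day 1, which is 56 days = 8 weeks. A subject with no platelet transfusion in it already satisfies the 8-week rule before the first dose.
2. Weight of one such subject: 1/8 = 12.5 points in an arm, 1/32 = 3.1 points overall.
3. Rate = u + (1 − u)p. The results for u = 0, 25, 50 and 75% are:

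| u | p = 0 | p = 10% | p = 50% | Difference, (1 − u)(50 − 10) |
|---|---|---|---|---|
| 0% | 0% | 10% | 50% | 40 points |
| 25% | 25% | 32.5% | 62.5% | 30 points |
| 50% | 50% | 55% | 75% | 20 points |
| 75% | 75% | 77.5% | 87.5% | 10 points |

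4. The p = 0 column assumes that no previously transfused subject has an 8-week free run. That is not the same as no drug effect: over 52, 104 or 156 weeks any single 8-week run is enough.
5. Comparing two values of p between randomized doses fits Weeks 1–8 only. From Week 9 non-responders are escalated and responders may be adjusted (Sections 6.1.2 to 6.1.2.2), so the other six of the seven windows mix doses.

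**The case against.** **Part B.** The strongest reply is that the plan makes no error here. The Definition of Terms and Section 12.1.1.2 give the same explicit rule, no subject is classified two ways, and both speak of achieving a transfusion-free period. Only the verb in the endpoint list suggests a change of status. This stands: part B is an improvement in interpretability. A reader might infer that the planned rate is known to be inflated, that it equals u when the drug does nothing, or that dose differences are diluted in every window. The documents support none of these. The untransfused share is not given and may be zero, the second inference also needs p = 0, and the third is clean only for Weeks 1–8. Arms of 8, split further, will also give very wide intervals.

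**Part A.** The reply is that the Definition of Terms governs and 12.1.1.2 merely abbreviates it. That is possible, but 12.1.1.2 does not refer back to the Definition of Terms for the limit, and it spells out the ANC limits in the very next sentence, which weakens the reading.

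**Both parts.** Section 12.5 promises a detailed SAP before database lock. That is a suitable place for the resolution, but the documents contain no text that supplies it.

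**Conclusion.** Part A holds as an inconsistency between two current texts. It affects any subject with pretreatment Hb of 9.0 g/dL or more who meets a response route. It reaches tri-lineage response only when baseline ANC is also below 1.0 × 10^9/L. How many subjects this involves is not given.

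Part B holds as a cheap improvement. As the rule is written, each subject with no qualifying transfusion before or during treatment is worth 12.5 points in an arm of 8. This follows from the rule, the PPS denominator and the absence of any baseline condition; no section states it outright. Its actual size is unknown and may be nil.

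Both parts concern secondary, descriptive endpoints. The primary endpoint, platelet response at Week 9, is untouched.

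**What to change.** **A.** In Section 12.1.1.2, carry over the pretreatment haemoglobin limit from the Definition of Terms so that one erythroid definition applies, and state whether it covers the transfusion-reduction route. Section 12.1 makes the total number of subjects the default denominator. Confirm that this holds here, and show the number evaluable at baseline beside each erythroid, neutrophil and tri-lineage rate.

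**B.** Keep the planned all-PPS proportion, described as platelet transfusion-free for at least 8 consecutive weeks. Add the same proportion in two exhaustive baseline groups, by dose for Weeks 1–8 and pooled over doses for all windows:

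- at least one qualifying platelet transfusion from Day −55 up to the first dose: report as became independent;
- none, which includes subjects with only non-qualifying transfusions: report simply as transfusion-free for at least 8 weeks. Calling this maintained independence would be wrong in the long windows, where a subject can be transfused on treatment and later have a free run.

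State how a transfusion on Day 1 is counted.

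**Cost.** Wording and one table. The endpoint label in the Synopsis and Section 3.3.1.2 may need a matching edit, so an amendment may be required. No new data are needed: Section 6.2.3 already records dates, pre-transfusion counts and reasons. The planned rate keeps its precision. With exact (Clopper-Pearson) 95% intervals, taken here because the plan names no method, 4/8 gives 15.7–84.3% and 16/32 gives 31.9–68.1%. The downside is in the subsets. If half are untransfused at baseline, 2/4 in an arm gives 6.8–93.2% and 8/16 pooled gives 24.7–75.3%. If three quarters are, 1/2 gives 1.3–98.7%. The by-dose figures are for description only.

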The present study will be conducted to evaluate the efficacy and safety of AMG531 and to determine the recommended initial dose of AMG531 on the basis of its efficacy and safety when it is administered SC, QW at a dose of 1, 3, 6 or 10 $\mu\text{g}/\text{kg}$ to the aplastic anemia patients with immunosuppressive-therapy refractory thrombocytopenia and also to assess the pharmacokinetics of this product during the initial dose evaluation period. Its efficacy and safety during the extension period will also be evaluated. Efficacy and safety of AMG531 in the long term treatment beyond 1-year will be further evaluated for those showing continuous responses after 1 year treatment.

III STUDY DESIGN

This is a multi-center, randomized, open-label, parallel, comparative, dose-finding study.

The overall study design is presented below.

IV STUDY SUBJECTS

AA subjects with thrombocytopenia refractory to immunosuppressive agents.

IV-1 Inclusion criteria

Subjects may be included in the study if they meet all of the following criteria:

- 1) Patients who have provided written informed consent of their free will to participate in this clinical study. Written informed consent must be obtained prior to performing any study-related procedure
- 2) The subject is able and willing to comply with study procedures and follow-up as described in the protocol and ICF
- 3) Males and female subjects ≥ 19 years of age at the time of obtaining informed consent
- 4) Eastern Cooperative Oncology Group (ECOG) performance status (PS) score of ≤ 2 at the time of screening
- 5) Diagnosis of AA, confirmed by bone marrow and cytogenetic studies
- 6) Patient who is refractory to immunosuppressive therapy (IST)
- 7) Prior treatment with at least one course of horse or rabbit anti-thymocyte globulin (ATG) with cyclosporine
- 8) Thrombocytopenia defined as platelet $\leq 30 \times 10^9/L$
- 9) Fulfilling all of the following criteria in the screening examination
 - T-Bilirubin ≤ 1.5 times the upper limit of the laboratory normal range
 - ALT and AST ≤ 3 times the upper limit of the laboratory normal range
 - Creatinine ≤ 2.0 mg/dL

IV-2 Exclusion criteria

Subjects must be excluded from participating in this study if they meet any of the following criteria:

- 1) Concurrent active infection not adequately responding to appropriate therapy
- 2) Human immunodeficiency virus positivity
- 3) Bone marrow reticulin grade of > 1 (Appendix 1)

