1 BACKGROUND AND STUDY RATIONALE

2 STUDY OBJECTIVES

The present study will be conducted to evaluate the efficacy and safety of AMG531 and to determine the recommended dose of AMG531 on the basis of its efficacy and safety when it is administered SC, QW at a dose of 1, 3, 6 or 10 µg/kg to the AA patients with immunosuppressive-therapy refractory thrombocytopenia and also to assess the pharmacokinetics of this product during the initial dose evaluation period. Its efficacy and safety during the extended period will also be evaluated. [REDACTED]

[figure not shown]
[REDACTED] - Efficacy and safety of AMG531 in the long term treatment beyond 1-year will be further evaluated for those showing continuous responses after 1 year treatment.

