3.3.1.2 Secondary endpoints

- The proportion of subjects achieving a platelet response any time during the initial dose evaluation period, Week1 through Week 12, Week 1 through Week 16, Week 1 through Week 24, and Week 1 through Week 52.
- The proportion of subjects who become platelet transfusion independent during the initial dose evaluation period, Week1 through Week 12, Week 1 through Week 16, Week 1 through Week 24, Week 1 through Week 52, Week 1 through Week 104, and Week1 through Week 156
- The proportion of subjects achieving erythroid response and/or neutrophil response during the initial dose evaluation period, Week1 through Week 12, Week 1 through Week 16, Week 1 through Week 24, Week 1 through Week 52, Week 1 through Week 104, and Week1 through Week 156
- Duration of platelet response
- Time to platelet response
- Changes in platelet count, hemoglobin concentration, and neutrophil count as continuous variables
- Changes in bone marrow cellularity and reticulin grade
- Changes in GIMEMA bleeding scale
- The proportion of subjects achieving tri-lineage responses
- The proportion of subjects able to discontinue study drugs after achieving normal level for 8 consecutive weeks without transfusion.
- Duration of study drug discontinuation while maintaining stable response

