5.4 Criteria for entering long-term treatment period

- 1) Subjects with platelet responses confirmed during 8 weeks prior to Week 53 (Week 46-Week 53)
- 2) Subjects who do not have any significant changes in medical condition during the initial evaluation period and extension period (Week 1-Week 52) including bone marrow stem cell disorders or new active malignancies

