11 STOPPING RULES AND PROCEDURES

11.1 Subject withdrawal

11.1.1 Criteria for subject withdrawal

Any of the following circumstances will result in the subject being withdrawn from the study:

- 1) The subject is found to be ineligible for participation in this study due to violations in the inclusion or exclusion criteria specified in the study protocol;
- 2) The subject decides to discontinue his/her participation in the study;
- 3) The subject becomes unable to undergo necessary observations or examinations;
- 4) The subject who does not achieve a platelet response after 8-week treatment with AMG531 20 µg/kg QW;
- 5) The investigator considers that the subject should be withdrawn from the study due to an adverse event (including progression of the primary disease);
- 6) The subject received any of the prohibited concomitant medications or treatments;
- 7) The subject becomes pregnant or wants to have children during the study;
- 8) The investigator assesses that the subject needs to be withdrawn from the study for any reason not specified above.
- 9) The subject who does not meet the entry criteria for long-term treatment period

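### The Week 1-104 and Week 1-156 transfusion-independence and erythroid/neutrophil proportions count anyone who ever qualified since Week 1, so they cannot fall and do not show whether those benefits last beyond one year

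*Combined protocol and SAP*

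**What the plan says.** Section 2 sets a long-term aim: "Efficacy and safety of AMG531 in the long term treatment beyond 1-year will be further evaluated for those showing continuous responses after 1 year treatment".

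The proportions that reach past Week 52 are listed in Section 3.3.1.2 and repeated in 12.1.1.2. Platelet transfusion independence and erythroid and/or neutrophil response are each reported over a series of windows ending in "Week 1 through Week 52, Week 1 through Week 104, and Week1 through Week 156". Platelet response itself has no listed proportion after Week 52.

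On the criterion for independence, 12.1.1.2 states: "Platelet transfusion independence is defined as achieving transfusion free period of at least 8 consecutive weeks". Erythroid response is met by a hemoglobin rise of at least 1.5 g/dL without transfusion, or by at least 4 fewer transfused units over 8 consecutive weeks. Neutrophil response is a doubling, or a rise above a fixed amount, depending on the starting count. Neither count-based criterion asks for confirmation or duration. No section requires the qualifying period or value to occur after Week 52, or to be present at Week 104 or 156.

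On the denominator, Section 12.1 expresses percentages relative to the total number of subjects. Membership of the per protocol set is decided on conduct in the initial dose evaluation period (12.6.2).

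On who continues, Section 5.4 admits to long-term treatment only subjects whose platelet response was confirmed in Weeks 46 to 53. Section 11.1.1 item 9 withdraws "The subject who does not meet the entry criteria for long-term treatment period".

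**The concern.** In a group selected for responding at one year, the question for years 2 and 3 is whether the benefit holds. A proportion that asks only whether a subject has qualified at any time since Week 1 cannot answer it. A subject who had one transfusion-free spell in Weeks 10 to 17, relapsed at Week 60 and was transfused weekly from then on still counts as transfusion independent in the Week 1-156 figure.

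At stake is how the long-term results are read. A flat or rising series from Week 52 to Week 104 to Week 156 looks like maintained benefit, yet the definition permits no other pattern. Since platelet response has no proportion after Week 52, these are the main long-term response rates in the plan.

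**Working it through.** The plan states no figure to reproduce here and gives no transfusion rates. All weekly probabilities below are assumptions that show the mechanism. They are not estimates for this trial.

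**1. The proportions cannot fall.** Let E(W) be the number of subjects who have qualified at least once in Weeks 1 to W, and N the fixed number in the analysis set. The windows are nested, so E(52) ≤ E(104) ≤ E(156). With the same N, the three proportions are ordered the same way. A simulation of 32,000 subjects (1,000 trials of 4 × 8 = 32) found no exception.

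**2. Benefit lost after one year.** Assume a weekly platelet transfusion probability of 0.10 to Week 52 and 0.60 afterwards, with weeks independent and everyone followed.
- Planned 'ever' proportion: 99.8% at Weeks 52, 104 and 156.
- Transfusion-free throughout the last 8 weeks: 0.9^8 = 43.0% at Week 52, and 0.4^8 = 0.07%, about 0.1%, at Weeks 104 and 156. The simulation gave 43.1%, 0.1% and 0.1%.

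**3. The proportions rise when nothing changes.** Take a constant weekly transfusion probability p. Let r_j(w) be the probability that, after w weeks, the current transfusion-free run has length j (0 to 7) and no 8-week run has yet occurred. Let A(w) be the probability that one has. Then r_0(w+1) = p × Σ r_j(w), r_{j+1}(w+1) = (1−p) × r_j(w) for j = 0 to 6, and A(w+1) = A(w) + (1−p) × r_7(w).

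| p | 8 weeks | 52 weeks | 104 weeks | 156 weeks |
|---|---|---|---|---|
| 0.2 | 16.8% | 91.4% | 99.4% | 100.0% |
| 0.3 | 5.8% | 61.7% | 86.9% | 95.5% |
| 0.4 | 1.7% | 28.1% | 50.4% | 65.8% |

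**4. Unconfirmed single counts.** If a count qualifies by fluctuation with probability f at each weekly visit, independently, the chance of at least one in W weeks is 1 − (1−f)^W. For f = 0.01 this is 40.7%, 64.8% and 79.2% at 52, 104 and 156 weeks. For f = 0.02 it is 65.0%, 87.8% and 95.7%. This applies to the hemoglobin and neutrophil routes only. The RBC-transfusion route needs 8 consecutive weeks, though it too need occur only once.

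**5. Scale in one dose group.** Suppose 6 of 8 subjects have a qualifying spell by Week 52 and enter long-term treatment, and 4 of the 6 return to regular transfusion at Week 60. The planned Week 1-104 and Week 1-156 figures are each at least 6/8 = 75%. Among entrants, 2/6 = 33% are transfusion-free in the last 8 weeks. On all 8 the figure is 2/8 = 25% if the two withdrawn subjects are counted as not free, and 4/8 = 50% if both are counted as free. Their status is unobserved, so 25% is a convention and not a measured share.

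**6. Do other planned summaries fill the gap?**
- Duration of platelet response (12.1.1.2) covers one lineage, with no definition of loss, gaps or censoring.
- Count changes at each visit (12.1.1.2) use only available counts. Counts soon after transfusion are excluded (12.1.1) and missing values are not imputed (12.4), so relapsed or withdrawn subjects tend to drop out.
- The bleeding scale is measured at Weeks 53, 77, 105 and 129 (8.2.4). It records bleeding, not transfusion status or response.
- The proportions reaching normal level, tapering and stopping drug, and the longest drug-free stable period (12.1.1.2), describe the best responders.

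Each is informative, but none gives the share transfusion-free, or in erythroid or neutrophil response, near Week 104 or 156.

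**The case against.** The strongest reply is that the endpoints are worded as things a subject becomes or achieves between Week 1 and a later week, so they are cumulative incidences on their face and mislead only someone who reads them as prevalence. That is fair, and labelling deals with the misreading. It does not supply the missing quantity: the objective concerns efficacy beyond one year, and no listed proportion measures it as a current state.

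A second reply is that these are descriptive secondary summaries. There are 8 subjects per group, no significance level (12.2), and a detailed SAP still to be finalized before database lock (12.5). This also stands: the Week 9 primary endpoint is untouched, and nothing is lost if the tables are added in time.

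Three stronger readings are tempting, and the documents do not support them.
- *The plan cannot show durability at all.* It can in part, through the summaries in step 6.
- *The later windows add little because entrants have already been counted.* The entry rule concerns platelet response. It says nothing about erythroid or neutrophil response, where first responses after Week 52 can be real and worth counting.
- *Every response can be claimed on one value.* The RBC-transfusion route cannot.

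The cumulative reading of the independence and erythroid/neutrophil endpoints is itself an inference. The phrase 'any time' is attached only to platelet response. But the wording of the other endpoints points the same way, and no section supports a sustained-response reading.

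**Conclusion.** The concern holds for these proportions. As defined, the Week 1-104 and Week 1-156 figures for platelet transfusion independence and for erythroid and/or neutrophil response cannot decline after Week 52, and they do not show whether these benefits persist. The discrepancy has no fixed size: it depends on how many subjects lose response, which the documents do not give. Under the assumed rates it ranges up to 99.8% against 0.1%. In the one-group illustration it is 75% against 33% of entrants.

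The conclusion rests on the fixed denominator of Sections 12.1 and 12.6. If only subjects still followed after Week 53 were counted, the figure could move. It would still not measure persistence, because it would still credit qualification at any time since Week 1. The point affects interpretation of a stated objective, not the primary result, and is worth correcting before the SAP is final.

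**What to change.** Keep the cumulative proportions and label them 'ever achieved by Week X'. Add current-status proportions at about Weeks 52, 104 and 156:

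1. Platelet transfusion-free, and separately RBC transfusion-free, throughout the 8 weeks ending at that time. Use the dated transfusion records (6.2.3) and the same rule for which transfusions count as in 12.1.1.2.
2. Platelet, erythroid and neutrophil response criteria met at the last usable scheduled count within a short pre-stated window that includes an odd-numbered visit. Examples are Weeks 51-53, Weeks 103-105, and Week 155 to the end-of-treatment visit.

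The window matters. Note 11 to the observation schedule lets subjects who stopped drug after reaching normal level skip even-numbered visits, and 104 and 156 are even. Unscheduled counts are barred (12.1.1) and missing values are not imputed (12.4), so scoring at those exact weeks could lose the most durable responders. Week 155 secures a count for them, because Section 8.2.5 ties the end-of-treatment visit to the last dose.

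Report both sets on the full analysis set, counting subjects withdrawn earlier as not in response. State this as a scoring convention because their status is unobserved. Report them also on long-term entrants alone. Base statements about efficacy beyond one year on these figures.

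The cost is SAP wording, a visit-window rule and a few tables from weekly hematology and transfusion data already collected. The long-term figures will probably look less favourable.
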